4.5.1.3 RAD001 Pharmacodynamic studies

Pharmacokinetic/pharmacodynamic modeling based on inhibition in a peripheral biomarker (S6 kinase inhibition in peripheral blood mononuclear cells) suggests that 5-10 mg daily should be an adequate dose to produce a high-degree of sustained target inhibition. Furthermore, molecular pharmacodynamic (MPD) studies using IHC in biopsied tumor tissue assessed the degree of inhibition and its duration (for p-S6, p-4E-BP1 and p-Akt expression) with the daily and weekly dosing. The pathologist was blinded for the biopsy sequence. There was almost complete inhibition of p-S6 at all doses and schedules studied (p=0.001). Preliminary results suggest a dose-related decrease in p-4E-BP1 and increase in p-Akt expression with maximal effect at 10 mg daily and ≥ 50 mg weekly. The study results are provided in Table 4-6.

Table 4-6 p-S6, p-4E-BP1 and p-Akt expression at various doses of RAD001

Dose of RAD001	p-S6 inhibition (mean %)	p-4E-BP1 inhibition (mean %)	p-Akt activation (mean %)

Daily 5 mg (n=3)	100.0	48.0	22.2
Daily 10 mg (n=6)	92.5	58.2	45.5
Weekly 20 mg (n=5)	96.7	5.9	32.7
Weekly \geq 50 mg (n=6)	100.0	63.8	63.1

Reference: RAD001 Investigator's Brochure 2005

4.5.1.4 Temozolomide

Temozolomide is available in 5mg, 20mg, 100mg, and 250mg capsules which are supplied in amber glass bottles with child-resistant polypropylene caps. The capsules should not be opened or chewed. They should be swallowed whole with a glass of water. Procedures for handling and disposal of anticancer drugs should be considered.

The dose of Temozolomide will be based on baseline BSA \pm 5%. The dose of temozolomide should be rounded down to the nearest dose available through combination of appropriate capsules. To facilitate patient administration of temozolomide, a simpler combination of pills is acceptable if the total dose is within \pm 5% of the calculated dose based on BSA. The exact dose administered will be recorded in the case report form (CRF). The dose of temozolomide will be recalculated when BSA changes $>5\%$ or $<5\%$ from baseline.

Temozolomide should be given with approximately 8 ounces of water over as short a time as possible. Patients should be instructed to swallow capsules whole and in rapid succession and to not chew capsules. If vomiting occurs during the course of treatment, no re-dosing of the patient is allowed before the next scheduled dose. Missed doses should not be repeated. It is recommended that patients take Temozolomide at bedtime and fast for 2 hours before each dose and continue fasting for 1 hour after each dose. Water is allowed during the fasting period.

4.5.2 Concomitant therapy

1. Patients on study therapy may be at risk for temozolomide-related selective lymphopenia and opportunistic infections. To reduce the risk of opportunistic infections, patients will receive prophylaxis with Bactrim DS, 1 tablet orally every Monday, Wednesday, and Friday. Patients allergic to Bactrim should be initiated on an alternate, standard PCP prophylaxis regimen. Prophylaxis will begin for all patients after completing their first cycle of therapy (approximately one month after beginning therapy).
2. Temozolomide may be emetogenic, and it is suggested that patients take compazine 10 mg po prior to each dose while beginning their treatment regimen. Other antiemetics may be utilized at the discretion of the treating physician. If patients appear to tolerate Temozolomide without nausea, the routine prophylactic use of compazine may be

discontinued. If refractory nausea develops, the use of prophylactic ondansetron should be considered.

3. All patients should be maintained on the same medications throughout the study period, as medically feasible.
4. The investigator should instruct the patient to notify the study staff about any new medications he/she takes after the start of the study drug. All medications (other than study drug/s) and significant non-drug therapies (including physical therapy and blood transfusions) administered after the patient starts treatment with study drug/s must be recorded.

4.5.3 Prohibited medications

1. Growth factors cannot be used to induce elevations in neutrophil count for the purposes of administration of Temozolomide on the scheduled dosing interval or to allow treatment with Temozolomide at a higher dose.
2. Use of erythropoietin is allowed.
3. No other investigational drugs will be allowed during the study.
4. Patients must be instructed not to take any additional medications (including over-the-counter products) during the trial without prior consultation with the investigator. All medications taken within 30 days of screening should be recorded. If concomitant therapy must be added or changed, the reason and name of the drug/therapy should be recorded.
5. In general, the use of any concomitant medication/therapies deemed necessary for the care of the patient are allowed, including drugs given prophylactically (e.g. antiemetics +/- steroids), with the following exceptions:
 - no other investigational therapy should be given to patients
 - no chronic treatment with systemic steroids or another immunosuppressive agent
 - no anticancer agents other than the study medications administered as part of this study protocol should be given to patients. If such agents are required for a patient then the patient must first be withdrawn from the study.
 - leukocyte growth factors (e.g. G-CSF and GM-CSF) are not to be administered systematically but may be prescribed by the investigator for severe neutropenia if this is thought to be appropriate.
 - no live vaccines should be administered to patient due to immunosuppressant potential of RAD001.
 - drugs or substances known to be inhibitors or inducers of the isoenzyme CYP3A (Table 4.7) cannot be administered in association with RAD001 as these can alter

metabolism. Strong inhibitors or inducers of the isoenzyme CYP3A cannot be administered as systemic therapy.

Table. 4.7 Clinically relevant drug interaction: substrates, inducers and inhibitors of isoenzyme CYP3A

Substrates		
Antibiotics: clarithromycin erythromycin NOT azithromycin telithromycin	Calcium Channel Blockers: amlodipine diltiazem felodipine nifedipine nisoldipine nitrendipine verapamil	
Anti-arrhythmics: quinidine	HMG CoA Reductase Inhibitors: atorvastatin cerivastatin lovastatin NOT pravastatin simvastatin	
Benzodiazepines: alprazolam diazepam midazolam triazolam	Miscellaneous: aripiprazole buspirone gleevec haloperidol (in part) methadone pimozide quinine NOT rosuvastatin sildenafil tamoxifen trazodone vincristine	
Immune Modulators: cyclosporine tacrolimus (FK506)		
HIV Protease Inhibitors: indinavir ritonavir saquinavir		
Prokinetic: cisapride		
Antihistamines: astemizole chlorpheniramine		
Inducers		
Carbamazepine Phenobarbital Phenytoin	Rifabutin Rifampin	St John's wort Troglitazone
Inhibitors		
Amiodarone Cimetidine Clarithromycin Diltiazem Erythromycin	Fluvoxamine Grapefruit juice Seville orange juice or product Indinavir Itraconazole Ketoconazole	Mibefradil Nefazodone Nelfinavir Ritonavir Troleandomycin Verapamil

Reference to published literature: <http://www.medicine.iupui.edu/flockhart/clinlist.htm> as of July 13, 2006

4.5.4 Treatment compliance

Records of study medication used, dosages administered, and intervals between visits will be recorded during the study. Drug accountability will be noted and patients will be asked to return all unused study medication.

5 Visit schedule and assessments

5.1 Visit schedule and assessments

5.1.1 Pretreatment evaluation

Tests to be performed within 28 days prior to initiation of therapy (if day 28 falls on a weekend or holiday the deadline may be extended to the next working day):

- Radiologic assessment of tumor burden by CT scan within 28 days prior to initiation of therapy.
- Assessment of secretory proteins within 28 days prior to initiation of therapy. All patients will undergo an initial assessment of chromogranin A. Measurement of gastrin, VIP, or other secretory proteins will also be performed depending on tumor type.

Tests to be performed within 14 days prior to initiation of therapy (if day 14 falls on a weekend or holiday, the deadline may be extended to the next working day):

- All patients will be assessed by history and physical examination, including height, weight, vital signs, and performance status within 14 days prior to initiation of therapy.
- Baseline hematological and biochemical profiles, including CBC with differential, platelets, and serum chemistries: fasting glucose, sodium, potassium, chloride, bicarbonate, creatinine, blood urea nitrogen, albumin, total protein, SGOT (AST), SGPT (ALT), total bilirubin, alkaline phosphatase, calcium, magnesium, phosphate.
- Serum pregnancy test for women of childbearing potential

5.1.2 Evaluations during treatment

5.1.2.1 Day 1 of every cycle

- Physical examination
- Toxicity assessment
- Vital signs
- Weight
- Serum chemistries

- CBC with differential

5.1.2.2 Day 15 of cycles 1 through 6 only

- Physical examination
- Toxicity assessment
- Vital signs
- Weight
- CBC with differential

5.1.2.3 Data to be obtained following every 2 cycles of treatment (time of restaging):

- Radiologic assessment of tumor burden by CT scan
- Assessment of serum chromogranin A and other secretory proteins (if applicable).

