Once the first cohort of patients completes the initial 35-day cycle without experiencing a DLT, the second cohort of patients will begin enrollment. The second patient cohort will consist of at least 3 patients who will receive an oral dose of 10 mg of RAD001 administered daily and an oral dose of temozolomide of 150 mg/m² daily for 7 days every other week beginning on Day 1 of RAD001 administration. The patients will be treated for a 28-day Treatment Period and then observed over a 7-day observation period for signs of treatment-emergent toxicity. Patients will not receive treatment with either RAD001 or temozolomide during the 7-day observation period. If patients do not exhibit disease progression or a dose limiting toxicity (DLT), as defined in section 3.3, they will receive subsequent 28-day cycles of treatment without additional 7-day observation periods. Patients in this cohort may be treated simultaneously without requiring previously enrolled patients to complete their first cycle of treatment and observation.

If a DLT is observed in 1 of the first 3 patients, 3 additional patients will be enrolled at that same dose level. If no additional DLT is observed after all patients have completed the first cycle of treatment and observation period, the trial will continue to enroll the third cohort of patients. If additional DLTs are observed, enrollment to the trial will be stopped and the study will be re-evaluated.

If a DLT is observed in 2 or more of the first 3 patients or of the total 6 patients during Cycle 1 of treatment, accrual to the trial will be suspended pending review of the events and revision of the protocol.

3.2.3 Cohort 3

Once the second cohort of patients completes the initial 35-day cycle without experiencing a DLT, the third cohort of patients will begin enrollment. The third patient cohort will consist of 32 patients who will receive an oral dose of the maximum tolerated dose of RAD001 administered daily and an oral dose of temozolomide of 150 mg/m² daily for 7 days every other week beginning on Day 1 of RAD001 administration. The patients will be treated for a 28-day Treatment Period. Patients who complete the initial cycle of therapy without evidence of significant treatment-emergent toxicity or progressive disease may receive additional 28-day cycles of treatment until the appearance of significant treatment-emergent toxicities or disease progression.

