4.3 Monitoring of suspected toxicities

Patients whose treatment is interrupted or permanently discontinued due to an adverse event or abnormal laboratory value suspected to be related to RAD001 or temozolomide must be followed at least weekly until the adverse event or abnormal laboratory resolves or returns to grade 1. If a patient requires a dose delay of > 21 days from the intended day of the next scheduled dose, then the patient must be discontinued from the study.

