4.4 Dose Modification

4.4.1 RAD001 dose adjustments

Three RAD001 dose levels are defined for dose adjustment: 10 mg daily, 5 mg daily, and 5 mg every other day.

Table 4.1.1 : Dose Reduction Schedule for RAD001 – Cohort 1

Dose Level	Dose and schedule	Days per cycle (cycle length = 28 days)
0	5 mg daily	Continuous
Decrease 1 dose level	5 mg every other day	Continuous
Decrease 2 dose levels	Discontinue therapy	

Table 4.1.2 : Dose Reduction Schedule for RAD001 – Cohort 2

Dose Level	Dose and schedule	Days per cycle (cycle length = 28 days)
0	10 mg daily	Continuous
Decrease 1 dose level	5 mg daily	Continuous
Decrease 2 dose levels	5 mg every other day	Continuous
Decrease 3 dose levels	Discontinue therapy	

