4.4.3 Dose reductions for hematologic toxicity

Cohort 1: If the ANC is $<1,000$ or the platelet count is $<50,000$ during study therapy, RAD001 and temozolomide will be delayed. If RAD001 or temozolomide cannot be administered on the scheduled day of dosing, the CBC will be repeated weekly for up to and including 3 weeks until the ANC is $\geq 1000/\text{mm}^3$ and the platelet count $\geq 50,000/\text{mm}^3$. At that time, temozolomide will be reinitiated at one reduced dose level ($100 \text{ mg}/\text{m}^2$ daily, see Tables 4.1-4.2). The dose of RAD001 will remain at 5 mg daily. For subsequent dose reductions, both temozolomide and RAD001 will be reduced by one dose level. If treatment is held more than 3 weeks, the patient should be taken off protocol therapy.

Cohort 2: If the ANC is $<1,000$ or the platelet count is $<50,000$ during study therapy, RAD001 and temozolomide will be delayed. If RAD001 or temozolomide cannot be administered on the scheduled day of dosing, the CBC will be repeated weekly for up to and including 3 weeks until the ANC is $\geq 1000/\text{mm}^3$ and the platelet count $\geq 50,000/\text{mm}^3$. At that time, RAD001 and temozolomide will be reinitiated at one reduced dose level (see Tables 4.1-4.2). If treatment is held more than 3 weeks, the patient should be taken off protocol therapy.

Growth factors cannot be used to induce elevations in neutrophil count for the purposes of administration of RAD001 and temozolomide on the scheduled dosing OR to allow treatment. Administration of erythropoietin is allowed.

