4.4.7 Management of non-infectious pneumonitis

Both asymptomatic radiological changes (grade 1) and symptomatic non-infectious pneumonitis (grade 2 = not interfering with activities of daily living or grade 3 = interfering with activities of daily living and oxygen indicated) have been noted in patients receiving RAD001 therapy. Non-infectious pneumonitis has been associated with RAD001 and other mTOR inhibitors (Atkins, 2004). In order to monitor for asymptomatic (grade 1) pulmonary infiltrates, a chest X-ray is required if a CT scan of chest is not used for bi-monthly disease evaluations. Additional chest X-rays/CT scans may be done, when clinically necessary. If non-infectious pneumonitis develops, consultation with a pulmonologist should be considered. Management of non-infectious pneumonitis suspected to be associated with RAD001 and dose modifications instructions are provided in Table 4.4.

Table 4.4 Management of non-infectious pneumonitis

Worst Grade Pneumonitis	Required Investigations	Management of Pneumonitis	Actions
Grade 1	CT scans with lung windows.	No specific therapy is required	Administer 100% of RAD001 and temozolomide doses.
Grade 2	CT scan with lung windows. Consider pulmonary function testing includes: spirometry, DLCO, and room air O ₂ saturation at rest. Repeat each subsequent Cycle until return to within normal limits. Consider a bronchoscopy.	Symptomatic only. Prescribe corticosteroids if cough is troublesome.	Discontinue study therapy until recovery to \leq grade 1. Study therapy may also be interrupted if symptoms are troublesome. If recovered, resume treatment with RAD001 and temozolomide at one lower dose level. Patients will be withdrawn from the study if they fail to recover to \leq grade 1 within 3 weeks.
Grade 3	CT scan with lung windows and pulmonary function testing includes: spirometry, DLCO, and room air O ₂ saturation at rest.; Repeat each subsequent Cycle until return to within normal limits. Bronchoscopy is	Prescribe corticosteroids if infective origin is ruled out. Taper as medically indicated.	Hold RAD001 and temozolomide until recovery to \leq grade 1. May restart RAD001 and temozolomide within 2 weeks at a reduced dose (by one level) if evidence of clinical benefit.

Worst Grade Pneumonitis	Required Investigations	Management of Pneumonitis	Actions
	recommended.		

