5.1.3.1 Table of required data

Table 5.1. Evaluation and visit schedule

Examination	Screening		Every Cycle	Cycles 1- 6	Every 2 cycles	End
	-28 days	-14 days	Day 1	Day 15		
Screening ^a		X				
History		X	X*	X		X
Physical Exam		X	X*	X		X
Vital Signs		X	X*	X		X
Height		X				
Weight		X	X*	X		X
ECOG PS		X	X*			X
Pregnancy Test ^b		X				
Hematology ^c		X	X*	X		X
Serum Chemistry ^d		X	X*			X
Serum Lipid Profile ^e		X			X	X
Radiologic Assessment of Tumor Burden ^f	X				X	X
Secretory proteins, serum chromogranin ^g	X				X	X
Prior/concomitant medication		X	continuous -----			
Adverse events		X	continuous -----			

* Screening tests do not need to be repeated for cycle 1.

^a Screening includes review of: demography/informed consent, inclusion/exclusion criteria, relevant medical history/concomitant medications, diagnosis and extent of cancer

^b For women of child-bearing potential: Women of childbearing potential must have a negative serum pregnancy test within 14 days of enrollment. Acceptable contraception should be used while on study and for at least 30 days after the last dose of RAD001.

^c Hematology must include: hemoglobin, hematocrit, platelets, total white blood cell count (WBC) and differential

^d Serum chemistry should be performed while fasting and include: fasting glucose, sodium, potassium, chloride, bicarbonate, creatinine, blood urea nitrogen, albumin, total protein, SGOT (AST), SGPT (ALT), total bilirubin, alkaline phosphatase, calcium, magnesium, phosphate.

^e Fasting serum lipid profile (repeated every three months) must include: total cholesterol, triglycerides, LDL, and HDL

^f Screening radiologic tests include abdominal and pelvic CT or MRI and must be done within 28 days of first RAD001 and temozolomide dose. Radiological scans documenting target lesions should be repeated every two months. If an initial observation of a partial or complete response is made, a confirmation scan should be done no sooner than 4 weeks and no more than 6 weeks after the initial observation. The same type of scan should be used at each evaluation.

^g Assessment of secretory proteins will be performed within 28 days prior to initiation of therapy.

6 Efficacy assessments

The primary efficacy endpoint is objective response rate as determined by radiology review. Important secondary endpoints are response duration and progression-free survival.

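### Restaging CT runs on two unreconciled clocks, treatment cycles and calendar months, so permitted dose holds may move the scans that date PFS and response

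*Combined protocol and SAP*

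**What the plan says.** **Cycle clock.** Section 5.1.2.3 lists the CT and the secretory proteins under "Data to be obtained following every 2 cycles of treatment (time of restaging". In Table 5.1 the radiology row is marked in the column "Every 2 cycles". Section 12.1.2 makes the Response Assessment Form due within 10 days after the cycle at which response is to be evaluated.

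**Calendar clock.** Footnote f, attached to that same radiology row, says "Radiological scans documenting target lesions should be repeated every two months". Section 4.4.7 agrees with it: "a chest X-ray is required if a CT scan of chest is not used for bi-monthly disease evaluations".

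**Cycle length and delays.** The dose tables in 4.4.1 give "Days per cycle (cycle length = 28 days". In Cohorts 1 and 2 the first cycle includes a treatment-free observation week; section 3.2.3 refers to it with "Once the second cohort of patients completes the initial 35-day cycle without experiencing a DLT". For low counts, 4.4.3 delays both drugs and "the CBC will be repeated weekly for up to and including 3 weeks". Section 4.3 removes a patient from study only beyond this limit: "If a patient requires a dose delay of > 21 days from the intended day of the next scheduled dose".

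**Endpoints.** Under 6.3, PFS ends at the first documented progression or death. Response duration starts when response criteria are first recorded as met and ends at documented progression. Section 6 names both as important secondary endpoints. The ± 2-day window in section 7 covers safety assessments; no window is given for efficacy scans.

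**The concern.** Two instructions for one scan, with no order of precedence, allow two sites in this multi-center study to comply fully and still scan on different days. The cycle clock carries a further risk. If a hold for toxicity postpones the end of the cycle, it also postpones the scan, and the date on which progression or response can be recorded then depends on how treatment was tolerated.

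At stake are the estimates of PFS, time to response and response duration. Section 10.2 plans Kaplan-Meier estimation for the first two, followed by multivariate analysis of related factors. Any factor associated with dose delay would carry some of this timing artefact. Scan dates cannot be corrected after the event.

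**Working it through.** No sample size, power or event figure in the plan rests on the restaging interval, so there is no stated figure to reproduce.

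**1. Intervals without holds**
- Two cycles: 2 × 28 = 56 days.
- Two months: 2 × 365.25 / 12 = 60.9 days.
- First interval in Cohorts 1 and 2: 35 + 28 = 63 days.
- By the sixth restaging: 6 × 56 = 336 days against 6 × 60.9 = about 365 days.

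**2. Intervals if a hold extends the cycle** (an assumption; the protocol is silent)
- One 21-day hold: 56 + 21 = 77 days.
- Two 21-day holds: 56 + 42 = 98 days. Table 4.2 has two reduced temozolomide levels before discontinuation, so two holds in one interval are possible.

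**3. Mean detection lag.** If progression is uniform within an interval of length L, the recorded date is late by L/2 on average:

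| L (days) | Mean lag (days) | Against 56-day grid |
|---|---|---|
| 56 | 28 | 0 |
| 60.9 | 30.4 | +2.4 |
| 77 | 38.5 | +10.5 |
| 98 | 49 | +21 |

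**4. The same patient on both grids.** Take one 21-day hold in the first interval. Fixed scans fall on days 56 and 112; the delayed scan falls on day 77. Progression in days 0–56 is recorded 21 days later. Progression in days 56–77 is recorded 35 days earlier, because the fixed grid would not find it until day 112. The mean is (56 × 21 − 21 × 35) / 77 = 441 / 77 = +5.7 days.

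After that interval the cycle grid is simply offset by 21 days. Of progressions, 35/56 are recorded 21 days later and 21/56 are recorded 35 days earlier. The mean is 0.625 × 21 − 0.375 × 35 = 0.

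**5. Average over patients with holds.** The documents give neither a PFS median nor a hold frequency, so these are assumed: exponential PFS with median 9, 15 or 24 months, and one or two 21-day holds within the first three scan intervals. In a simulation of 200,000 patients against a fixed 56-day grid:
- Mean recorded PFS among patients with holds moved later by 0.7 to 3.7 days.
- With one hold, 57% to 61% of dates were later and 30% to 34% earlier. With two holds, 58% to 68% were earlier, although the mean was still slightly later.
- The median is read off scan dates and so moves in steps. With 20% to 100% of patients having holds, it differed from the fixed-grid median by anything from 35 days earlier to 42 days later, with no consistent direction.

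**6. Response.** With an assumed PFS median of 15 months and mean time to response of 60 or 120 days, time to response lengthened by 1.4 to 13.4 days. Mean response duration changed by −0.4 to −12.2 days. Individual durations went both ways: 11% to 54% were longer and 27% to 56% shorter, depending on when the hold fell.

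**The case against.** The best defence is that there is only one clock. Footnote f sits on the radiology row itself, 4.4.7 uses the same calendar language, and the cycle column is just the nominal visit slot. Nothing says that a hold stops the cycle count or moves a scan. This is a fair reading, but the text does not compel it: 5.1.2.3 defines the time of restaging by cycles, and 12.1.2 ties the response form to a cycle. Each clock has support in more than one place.

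It is also fair to say that little depends on this. The study is single-arm, so there is no comparison to bias. The two-stage rule in 10.1 counts responses, and footnote f fixes the confirmation scan at 4 to 6 weeks by calendar. The observation week contributes almost nothing: 63 against about 61 days, in at most 12 patients. All of that stands.

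A reader might go further and infer that delays lengthen both PFS and response duration, by about 3 weeks per affected interval, in the patients who tolerate treatment worst. The documents do not support this:
- The 3 weeks (49 − 28 = 21 days) requires two maximal holds and progression within one interval. A patient progresses once, so it does not accumulate.
- Response duration has a scan-dated start as well as a scan-dated end, so a late scan can shorten it.
- Delays beyond 21 days (4.3) and grade 4 non-hematologic toxicity (Table 4.3) end participation or protocol therapy, and an end-of-study scan is scheduled (5.1.3). The patients affected are those with permitted holds who continue.

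**Conclusion.** The inconsistency is plain in the text, within a single row of Table 5.1, and should be reconciled. That part needs no assumption.

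The link to toxicity is conditional on a hold extending the cycle, which the protocol neither states nor rules out. On that reading one maximal hold stretches the interval from 56 to 77 days (mean lag +10.5 days), and two stretch it to 98 days (+21 days, the worst case for 28-day cycles). The resulting distortion falls on secondary, descriptive estimates. Mean PFS is slightly later, by days across patients with holds; time to response is later; response duration moves in either direction. The simulated sizes rest on the assumed medians, response times and hold patterns. The response-rate conclusion is largely unaffected. This is a cheap improvement, not a threat to the primary result.

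**What to change.** State one calendar clock and use it in 5.1.2.3, the Table 5.1 column, footnote f and 4.4.7. For example: tumor assessment every 8 weeks ± 7 days, counted from cycle 1 Day 1, regardless of dose delays or the observation week. Eight weeks matches two undelayed cycles but is not two months, so the footnote and 4.4.7 must be reworded as well.

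Two consequential edits are needed. Tie the Response Assessment Form in 12.1.2 to the scan date instead of the end of a cycle, and say whether chromogranin A and the other secretory proteins move with the scan or stay with the cycle. Leave the 4 to 6 week confirmation scan as it is.

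The cost is a few lines of wording, with no change to dosing rules or sample size. The small downside is that a scan may fall mid-cycle for a patient whose treatment was delayed.
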